4 STUDY DESIGN

4.1 OVERALL DESIGN

This study is a randomized, double-blinded, placebo-controlled trial of 60 parent and child combinations i.e. 60 parents and 60 children.

Participants will be randomized into one of two arms. This study will be double-blinded; the study participants and study coordinators will be blinded to the intervention or product allocation. Arm 1 will take NuBest Tall Growth Protein Powder throughout the trial. Arm 2 will take a placebo product for the duration of the trial. Only the children will take the test product.

The parents will answer questionnaires at Baseline and on Month 1, Month 2, Month 3, Month 4, Month 5, and Month 6. Parents will provide height and weight measurements of the child at Baseline, Month 2, Month 4, and Month 6. The children will complete cognitive assessments at Baseline and Month 6. The trial will be a virtual study consisting of only virtual assessments, and the participants will follow the use instructions provided by the research team.

4.2 SCIENTIFIC RATIONALE FOR STUDY DESIGN

To best understand the actual benefits of the test product without the influence of a potential placebo effect, a randomized, placebo-controlled, double-blinded study design is the gold-standard method. A 6-month study duration provides sufficient time for the test product to provide metabolic effects that may lead to enhanced health outcomes.

The data collection intervals for this trial were chosen to minimize the participant burden while still collecting valuable data about the efficacy of the test product. In addition to subjective data collected from questionnaires, height and weight measurements using a standardized tool will provide a non-biased, independent assessment of changes in height and weight across both groups. In addition, the cognitive assessments will provide an objective measurement of changes in cognitive function.

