1.1 SYNOPSIS

Title:	A Randomized, Double-blind, Placebo-controlled Study to Evaluate the Effects of a Dietary Supplement on Children's Health Outcomes
	This is a virtual, two-armed, randomized, double-blinded, placebo- controlled clinical trial that will last 6 months. Participants will take the NuBest Tall Growth Protein Powder or a placebo product daily.
Study Description:	The children's parents will complete questionnaires at baseline and regularly during the study period (Month 1, Month 2, Month 3, Month 4, Month 5, and Month 6).
	The children will complete cognitive assessments at home at Baseline and Month 6 (Endline).
	Parents will also provide height and weight measurements of the children at Baseline, Month 2, Month 4, and Month 6.
	Primary Objective: To examine the effect of the NuBest Tall Growth Protein Powder on cognitive function.
Objectives:	Secondary Objective: To investigate the impact of the NuBest Tall Growth Protein Powder on a range of health parameters, including height, weight, energy levels, immune function, and digestion.
	Primary Endpoint: The primary endpoint of this study is an improvement in cognitive function. Cognitive battery testing scores will be compared across the trial measurement points.
Endpoints:	Secondary Endpoints: The secondary endpoint is an increase in a range of parameters associated with health, including height, weight, energy levels, immune function, and digestion. Parents will provide height and weight measurements for the children and will complete questionnaires evaluating other health outcomes.
Study Population:	This study will recruit 60 participants (60 pairs of parents + child). The parents may be of any age group, the children must be aged as follows: Boys: 12 to 16 years Girls: 10 to 14 years
	Arm 1: Intervention - 30 participants

	Arm 2: Placebo - 30 participants		
Description of Sites/Facilities Enrolling Participants:	Virtual		

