Description of Study Intervention:	 After eligibility is established, participants will complete a Baseline questionnaire, the Baseline cognitive assessment, and provide the Baseline height and weight measurements. Participants will be randomly allocated to either the intervention or placebo group. The participants and Citruslabs will not be informed who is in the test or the placebo group. Participants will begin taking their respective product for 6 months. The children will drink one scoop of the powder mixed with 6-8 oz of water, milk, or smoothies. Parents will complete questionnaires at the end of Month 1, Month 2, Month 3, Month 4, Month 5, and Month 6, and will provide further height and weight measurements at Month 2, Month 4, and Month 6. The children will repeat the cognitive assessments at Month 6 (endline). 		
Study Duration:	6 months		
Participant Duration:	6 months		
Product Instructions:	 The test products must be consumed in the morning. Combine one scoop of the powder with 6-8 oz of water, milk, or smoothies. Do not use NuBest Protein Powder for baking or cooking recipes. 		
Stadiometer Instructions:	 Step 1: Upon powering on the device, securely affix it to the wall, ensure that the height measuring instrument remains perpendicular to the ground and parallel to the wall at a 90-degree angle. Step 2: Once you've adjusted the height accordingly, press the measurement key only in the absence of any obstacles. Choose a flat ground without steps, and try to avoid testing on carpets or uneven areas with plush carpets or rugs. Ensure the device is perpendicular to the ground. 		
Compensation	\$150 Visa gift cardFitBit Smart Scale		

Ultrasonic Height Measuring Stadiometer

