5 STUDY POPULATION

5.1 INCLUSION CRITERIA

To be eligible to participate in this study, an individual must meet all of the following criteria:

- 1. A parent of a child within the following age ranges:
 - Boy: 12 to 16 years
 - Girl: 10 to 14 years
- 2. Interested in their child trialing a dietary supplement designed to improve overall health outcomes in children, including height, maintenance of a healthy weight, cognitive function, immune function, and energy levels.
- 3. Willing to refrain from giving their child any vitamins, minerals, or herbal supplements of any kind for the duration of the study
- 4. Parents willing to weigh and measure the height of their child throughout the study
- 5. Generally healthy do not have any uncontrolled chronic disease

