6.7 REQUIRED DEVICES

Participants require access to a computer, laptop, or tablet to complete the cognitive assessments.

All participants will be provided with the FitBit Smart Scale and the Ultrasonic Height Measuring Stadiometer required for the height and weight measurements.

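### Height is read by parents at home with no rule on number of readings, averaging or time of day; three readings in a fixed window would cheaply sharpen the six-month gain.

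*Combined protocol and SAP*

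**What the plan says.** Section 4.1 sets the setting and the schedule: "The trial will be a virtual study consisting of only virtual assessments", and "Parents will provide height and weight measurements of the child at Baseline, Month 2, Month 4, and Month 6". Section 5.1 makes it an entry condition that there be "Parents willing to weigh and measure the height of their child throughout the study". Section 6.7 supplies the equipment: "All participants will be provided with the FitBit Smart Scale and the Ultrasonic Height Measuring Stadiometer required for the height and weight measurements".

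The only measurement procedure is the Stadiometer Instructions in the Synopsis (section 1.1). They cover fixing the device to the wall, keeping it upright, using a level, uncarpeted floor, and when to take the reading: "press the measurement key only in the absence of any obstacles". Nothing there or elsewhere gives a number of readings, a rule for combining them, a time of day, or what to do when readings disagree. The one time-of-day rule concerns the product: "The test products must be consumed in the morning". Section 4.4 speaks of the Month 6 height measurement in the singular, but that is not a rule on readings. The only stated check on entered values is the automatic range checks in section 8.4.

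Height is one of five parameters in the secondary endpoint: "The secondary endpoint is an increase in a range of parameters associated with health, including height, weight, energy levels, immune function, and digestion". Section 4.2 says that the tool-based readings "will provide a non-biased, independent assessment of changes in height and weight across both groups".

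**The concern.** The outcome of interest is a gain, that is, one height subtracted from another. The error of the Baseline reading and the error of the Month 6 reading both stay in that difference. A parent who follows the protocol to the letter may take one reading at each end, at whatever hour suits. The range checks would not normally catch an error of about a centimetre, because the resulting height is still plausible.

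What is at stake is precision. With 30 children per arm, and no effect size, SD or power given in section 5.4, any avoidable noise in the gain widens the interval for the height comparison. Section 7 also plans to report percentages of people who improved, and reading error can put an individual child on the wrong side of such a count. The device stays in the home, so repeat readings need no new equipment, visit or staff.

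**Working it through.** **The plan's own figure.** Section 5.4 states 60 participants, 30 per arm. It cannot be reproduced, because no SD, effect size, alpha or power is given. Section 7 gives no specific analysis for height.

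**Inputs from the protocol.** 30 per arm (section 5.4), equal allocation (section 6.3), height at Baseline and Months 2, 4 and 6 (section 4.1).

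**Assumed inputs, not in the documents.** SD of the true six-month gain, g, 1.0 to 1.5 cm. SD of the error of one home reading, e, 0.3 to 1.0 cm. For detectable differences: two-sided alpha 0.05, 80% power, no dropout.

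**Formulas.**

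- One reading at each end: Var = g² + 2e².
- Mean of three per visit, errors independent between readings: Var = g² + 2e²/3.
- Mean of three, half the error variance shared by all readings at a visit but independent between visits: Var = g² + 2(e²/2 + e²/6) = g² + (4/3)e².
- Worth in children: the one-reading variance divided by the three-reading variance. This is the factor by which the sample would have to grow to give the same precision with single readings.

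| g (cm) | e (cm) | Var, one reading | Var, three, independent | Ratio | Var, three, half shared | Ratio |
|---|---|---|---|---|---|---|
| 1.0 | 0.3 | 1.18 | 1.06 | 1.113 | 1.12 | 1.054 |
| 1.0 | 0.5 | 1.50 | 1.17 | 1.286 | 1.33 | 1.125 |
| 1.0 | 1.0 | 3.00 | 1.67 | 1.800 | 2.33 | 1.286 |
| 1.5 | 0.3 | 2.43 | 2.31 | 1.052 | 2.37 | 1.025 |
| 1.5 | 0.5 | 2.75 | 2.42 | 1.138 | 2.58 | 1.065 |
| 1.5 | 1.0 | 4.25 | 2.92 | 1.457 | 3.58 | 1.186 |

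The gain from three readings therefore runs from 5% to 80% with independent errors, and from 2.5% to 29% with half the variance shared.

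**Detectable difference at 30 per arm.** (1.960 + 0.842) × √(2/30) = 0.723 SDs of the gain (normal approximation).

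- g = 1.0, e = 0.5: 0.89 cm with one reading; 0.78 cm with three, independent; 0.84 cm with three, half shared.
- g = 1.0, e = 1.0: 1.25 cm; 0.93 cm; 1.10 cm.
- g = 1.5, e = 0.3: 1.13 cm; 1.10 cm; 1.11 cm.

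A t-based multiplier of 0.736 gives nearly the same picture: 1.27 and 0.95 cm in place of 1.25 and 0.93 cm.

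**Do Months 2 and 4 already serve as replicates?** Hardly. For a straight line through months 0, 2, 4 and 6, the squared deviations from the mean of 3 sum to 9 + 1 + 1 + 9 = 20. The error variance of the fitted six-month change is 36e²/20 = 1.8e², against 2e² from the two end readings. At g = 1.0 and e = 1.0 the detectable difference is 1.21 cm instead of 1.25 cm.

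**The case against.** The best case for the plan is that it is not without standardization. Every family has the same type of device, the instructions address mounting and floor, fixing the device to the wall goes much of the way to a constant spot, and range checks may catch gross misreads. The protocol does not prescribe a single reading; it is silent on the number. Height is secondary, so the primary cognitive endpoint is untouched. Section 4.2 says that the data collection intervals were chosen to limit participant burden. All of this stands, and it makes the point an improvement rather than a flaw that threatens the trial.

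The size is also open. Every SD above is an assumption, and at the low end the benefit is negligible. The 80% figure needs the largest assumed error and full independence between readings taken minutes apart. Time of day and device placement are likely to be shared by such readings, and averaging does not remove shared error.

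Several stronger readings are tempting, and the documents do not support them:

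- *That the between-arm height comparison is biased.* Participants and coordinators are blinded (sections 4.1 and 6.3), so random reading error should be similar in both arms. It widens the contrast without shifting it.
- *That section 4.2 falsely claims an independent assessor.* In context, *independent* contrasts tool readings with questionnaire answers, as it does in the section 3 table. The word could be clearer, but it is not shown to be wrong.
- *That a misread could equal the effect sought.* No target effect for height is stated.
- *That parents are untrained.* Training is not mentioned either way, and section 4.1 refers to instructions from the research team.
- *That height outranks the other secondary parameters.* Nothing in the plan ranks them.

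**Conclusion.** The point holds as a cheap improvement to a secondary endpoint. Followed as written, the protocol allows one home reading per visit at any hour, which puts twice the reading-error variance into the six-month gain. For a true SD of gain of 1.0–1.5 cm and a reading-error SD of 0.3–1.0 cm, both assumed, averaging three readings is worth at most 5–80% more children, with 29% at 1.0 and 0.5 cm. If half the error variance is shared within a visit, it is worth about 2.5–29%, with 12.5% at 1.0 and 0.5 cm. The documents cannot show where in these ranges the trial lies. The loss is one of precision only, given intact blinding.

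**What to change.** Add to the Stadiometer Instructions in section 1.1:

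- three height readings at Baseline and at Months 2, 4 and 6, with the child stepping away between readings;
- the same time-of-day window and the same mounting spot at all four time points, so that error common to a visit tends to cancel in the gain;
- entry of all three values, with their mean as the analysed height;
- a prompt to repeat the readings if any two differ by more than a limit set in advance.

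Optionally, reword *independent* in section 4.2 to say that parents take the readings with a standardized device. *Non-biased* need not be deleted on this ground.

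The cost is a few minutes per family at each of four time points, two extra data fields per time point (2 × 4 = 8 in all) and one programmed prompt. No staff, visits or devices are added. The change must be in place before Baseline readings are taken, because Baseline cannot be measured again later.

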4.3 JUSTIFICATION FOR DOSE

The test product examined in this study will be taken in the exact dosage of the commercially available product. This will be done to help establish marketing claims that can be used with the test product and to understand the current formulation of the test product.

4.4 END OF STUDY DEFINITION

A participant is considered to have completed the trial if they have completed all study phases, including the last scheduled assessments: Month 6 questionnaire, weight measurements, height measurement, and cognitive assessment.

5 STUDY POPULATION

5.1 INCLUSION CRITERIA

To be eligible to participate in this study, an individual must meet all of the following criteria:

- 1. A parent of a child within the following age ranges:
 - Boy: 12 to 16 years
 - Girl: 10 to 14 years
- 2. Interested in their child trialing a dietary supplement designed to improve overall health outcomes in children, including height, maintenance of a healthy weight, cognitive function, immune function, and energy levels.
- 3. Willing to refrain from giving their child any vitamins, minerals, or herbal supplements of any kind for the duration of the study
- 4. Parents willing to weigh and measure the height of their child throughout the study
- 5. Generally healthy do not have any uncontrolled chronic disease

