2 INTRODUCTION

2.1 STUDY RATIONALE

Protein is fundamental to growth and the repair of body tissues; hence, its adequacy in children's diets is critical for optimal physical development. Studies have highlighted the role of dietary protein in increasing height and weight in children, suggesting a direct correlation between protein intake and growth metrics¹⁻³. Similarly, essential vitamins such as Vitamin A, C, D, E, and B-complex and minerals like Calcium, Iron, and Zinc have well-documented contributions to other aspects of physical development, bone health, immune function, and cognitive development^{4,5}. For instance, Vitamin D's role in bone mineralization is well-documented⁶, while Iron and Zinc have been associated with cognitive function and immune defense⁷ Furthermore, emerging research on the gut-brain axis underscores the significance of digestive health in cognitive and immune system functions, advocating for the inclusion of probiotics and prebiotic fibers in dietary regimens for children⁸.

In the USA, many people are at risk of vitamin, mineral, and/or other micronutrient deficiencies⁹⁻¹¹. Children and adults are consuming more low-nutrient foods with added sugar and excess fats as compared to healthy, high-quality calories and micronutrients. The risk of this is further exacerbated by socioeconomic and family income to poverty ratio¹⁰. However, research has suggested that dietary supplements can be helpful in meeting nutrient requirements for some micronutrients.

With this in mind, the test product has been developed and contains a proprietary blend of vitamins, minerals, and probiotics designed to enhance children's and teenager's health outcomes through the aforementioned mechanisms. This study will assess the effects of the test product on a range of health outcomes in children over the course of 6 months.

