6.2 INTERVENTION FORMULATION

Intervention Product: Protein, Vitamin A, Vitamin C, Vitamin D, Vitamin E, Thiamine, Riboflavin, Niacin, Vitamin B6, Folate, Vitamin B12, Biotin, Pantothenic Acid, Choline, Calcium, Iron, Phosphorus, Iodine, Magnesium, Zinc, Selenium, Copper, Chloride, Sodium, Potassium, Organic Flax Seed Powder, L-Taurine, Inositol Hexanicotinate, L-Arginine, Bacillus subtilis DE111® Complex (1 Billion CFU) (Probiotic), Eucommia Bark Extract, Vitamin K, Whey Protein Concentrate, Chocolate Bean Powder Processed with Alkali, Organic Evaporated Cane Sugar, Milk Protein Concentrate, Guar Gum Powder, Natural Flavor, Potassium Chloride, Silicon Dioxide, Rebaudioside A (from Stevia Leaf Extract), Sucralose.

Placebo Product Ingredients: Maltodextrin, Guar gum powder, Silicon dioxide, Cocoa powder, Natural creamy vanilla flavor, Organic evaporated cane sugar, Stevia leaf extract, and Sucralose.

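### The supplement restriction omits protein, amino-acid and probiotic products, so either arm may take components of the test product, which could dilute the contrast with placebo

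*Combined protocol and SAP*

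**What the plan says.** Section 5.1, criterion 3, requires parents to be "Willing to refrain from giving their child any vitamins, minerals, or herbal supplements of any kind for the duration of the study". No other supplement rule appears. The exclusion criteria (5.2), the product instructions in the synopsis (1.1) and the intervention steps (6.1) do not mention outside supplements. The withdrawal rules (6.4) address new drugs and antibiotics but not supplements.

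Section 6.2 opens the test formulation with "Intervention Product: Protein, Vitamin A, Vitamin C, Vitamin D" and later lists "Bacillus subtilis DE111® Complex (1 Billion CFU) (Probiotic), Eucommia Bark Extract, Vitamin K, Whey Protein Concentrate". Milk protein concentrate, taurine and arginine are also listed. The placebo list begins "Placebo Product Ingredients: Maltodextrin, Guar gum powder, Silicon dioxide, Cocoa powder" and continues with flavor, sugar and sweeteners. It contains no protein ingredient, amino acid or probiotic.

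The rationale (2.1) relies on two of these components. On protein, it describes studies "suggesting a direct correlation between protein intake and growth metrics". On the gut-brain axis, it describes research "advocating for the inclusion of probiotics and prebiotic fibers in dietary regimens for children". It says that the product "contains a proprietary blend of vitamins, minerals, and probiotics".

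Section 7 adopts an intent-to-treat analysis that keeps every randomized child, whether or not the child complied.

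**The concern.** The protocol has already decided that outside supplements threaten its comparison, because it restricts some of them. The restricted classes do not match the product. Section 2.1 describes the blend by three classes, and criterion 3 covers the first two but omits probiotics. It also omits protein, which gives the product its name and is the mechanism that section 2.1 offers for height and weight.

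Outside use is plausible. Criterion 2 recruits parents who are interested in a supplement for height, weight, cognition, immunity and energy. The children are 10 to 16 years old, and the trial is run remotely over six months. A family that already gives a plain protein shake or a daily probiotic can continue.

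Two things are at stake. The treatment contrast may be smaller than designed. In addition, because such use is not a deviation, nothing visible requires it to be recorded, so the analyst may be unable to tell whether it happened.

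**Working it through.** **Step 1: match the formulation against the rule.**

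| Component | Test product (6.2) | Placebo (6.2) | Named in rationale (2.1) | Restricted by criterion 3 (5.1) |
|---|---|---|---|---|
| Vitamins, minerals | yes | vitamins and minerals not listed as such | yes | yes |
| Herbal extract (eucommia) | yes | no | no | yes |
| Protein (whey, milk) | yes | no | yes, for growth | no |
| Probiotic | yes | no | yes, for cognition and immunity | no |
| Amino acids (taurine, arginine) | yes | no | no | no |

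The last three rows are the gap.

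**Step 2: when does the gap change the between-arm difference?** Let E be the true effect of the product. Let c be the share of placebo children using an outside product and f the share of E that it gives them. Let c₁ be the share of active-arm children using one and g the extra share of E that they gain. Then

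expected difference = E × (1 − c·f + c₁·g).

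- Balanced use with additive effects (c₁ = c, g = f): the difference is E, with no dilution.
- Saturation, where active-arm children gain nothing extra (g = 0): the difference is E × (1 − c·f).
- Additive effects with unequal use (g = f): the difference is E × (1 − f·(c − c₁)), which is diluted only if placebo families use more.

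**Step 3: size under saturation.** The documents give no value for c or f, so both are assumptions. In information terms, the 60 children are worth 60 × (1 − c·f)² children in a trial without outside use.

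| c | f | Shrinkage c × f | 60 × (1 − c·f)² |
|---|---|---|---|
| near 0 | any | near 0 | about 60 |
| 0.2 | 0.25 | 5% | 60 × 0.95² = 54.2 |
| 0.2 | 0.5 | 10% | 60 × 0.90² = 48.6 |
| 0.3 | 0.5 | 15% | 60 × 0.85² = 43.4 |

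Setting f = 1 is an upper bound. It would require a protein or probiotic product to match the whole blend, although the vitamin, mineral and herbal parts remain restricted.

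**Step 4: what this means for power.** Section 5.4 states 60 children, 30 per arm, but gives no significance level, power, effect size or standard deviation (SD), so its figure cannot be reproduced. For illustration only, assume a two-sided 5% test of two means by the normal approximation. With 30 per arm, 80% power corresponds to (1.960 + 0.842) × √(2/30) = 0.723 SD. Starting from there:

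- Shrinkage of 5% gives 0.687 SD and about 76% power.
- Shrinkage of 10% gives 0.651 SD and about 71% power.
- Shrinkage of 15% gives 0.615 SD and about 66% power.

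**The case against.** The strongest reply is that the rule is the same in both arms and allocation is random and blinded (6.3), so outside use should be about equal. With additive effects the mean difference is then untouched. This stands: dilution needs saturation or greater use among placebo families. Saturation is plausible, since an active-arm child already receives protein and a probiotic daily, but the documents do not show it.

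Second, only part of the product can be duplicated. For cognition, the primary endpoint, section 2.1 names iron and zinc, which are restricted. The unrestricted route that it names for cognition is probiotics. It links protein to height and weight, which are secondary. This also stands, and it is why large values of f are hard to defend.

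Third, both arms may mix the powder with milk or smoothies (1.1, 6.1), and section 7 states an aim close to ordinary use, so background protein was never tightly controlled. This is fair. It argues for leaving ordinary food alone, but not for leaving supplement classes undefined.

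Fourth, the qualifier at the end of criterion 3 might be meant to cover every supplement, and a fortified shake would arguably be caught already. Grammatically the qualifier attaches to the three named classes, and the possible double reading is itself a reason to reword. The questionnaires and the full use instructions are not reproduced, so an item on supplement use may already exist.

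**Conclusion.** The gap is real and can be read directly from the text: children in either arm may take protein, amino-acid or probiotic products throughout without breaching a visible rule. The consequence is a possible dilution of unknown size. It is 5% to 10% if 20% of placebo children use such a product, it delivers a quarter to a half of the full effect, and active-arm users gain nothing. It is negligible if use is rare, and zero on average if use is balanced and effects add.

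A reader might infer that every between-arm difference is biased toward zero, or that outside use cancels the designed contrast. The documents do not support either reading. The rule is common to both arms, and most of the formulation remains restricted. Nor can it be said that the rule permits the product's active ingredients: section 6.3 mentions active ingredients without naming them. A null result would already be hard to interpret, because section 5.4 gives no basis for the sample size. This gap adds to that difficulty by an amount that cannot be stated.

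This is a cheap improvement to the design and does not invalidate the trial.

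**What to change.** Extend criterion 3, for both arms, to protein powders or shakes, amino-acid supplements and probiotic supplements other than the study product. State that ordinary foods, and the milk or smoothies permitted for mixing, are unaffected.

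Add one item on use of such products to the monthly parent questionnaires, if none is there already. Log a positive answer as a protocol deviation and keep the child in the intent-to-treat analysis. Use can then be reported by arm, and a sensitivity analysis by reported use can be pre-specified.

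The cost is one reworded criterion and one questionnaire item, with no change to sample size or assessment times. The downside is that a few families already using such products may decline to join.

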2.2 RISK/BENEFIT ASSESSMENT

Immediate risks:

There are no predicted risks associated with this product. However, some people may experience adverse reactions when trying a new product. NuBest Tall Protein contains milk-based ingredients, so it is not suggested for those with a dairy allergy. It does not contain soy, grain, wheat, GMO, or gluten.

As dairy can interact with a number of medications, all medications should be separated by a minimum of 4 hours from taking the test product.

Long-term risks:

There are no predicted long-term risks related to using this product. Any short-term risk should dissipate after discontinuing the test product.

Immediate benefits:

Participants may experience positive changes in overall health. Also, participants might experience increased energy levels, immune function, and overall well-being.

Long-term benefits:

Participants may experience an increase in height, maintenance of a healthy weight, and enhanced quality of life due to an increase in overall health.

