5.2 EXCLUSION CRITERIA

An individual who meets the following criteria will be excluded from participation in this study:

- 1. Any child with a history of endocrine disorder, heart disease, lung disease, kidney disease, digestive disease or skeletal dysplasia.
- 2. Any pre-existing chronic conditions that would prevent participants from adhering to the protocol, including oncological and psychiatric disorders.
- 3. Is undergoing or planning to undergo significant medical procedures in the next six months.
- 4. A history of severe allergic reactions, including but not limited to any of the product's ingredients.
- 5. Any child with a dairy allergy or lactose intolerance.
- 6. Has undergone any surgeries or invasive treatments in the last six months.
- 7. Has had any major illness in the last three months.
- 8. Having any planned invasive medical procedures during the study period
- 9. Currently participating in any other clinical study.
- 10. Unwilling to follow the study protocol.
- 11. Any child diagnosed with attention-deficit disorder (ADD) or attention-deficit hyperactivity disorder (ADHD).
- 12. Any child currently taking, or have they taken in the last 3 months, any prescription medication targeting ADD or ADHD (such as Adderall, Concerta, Focalin, Evekeo, or Ritalin).
- 13. Any child that is a 'fussy' eater or who the parent suspects may not tolerate consuming the test product daily for six months.

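### Inclusion criterion 3 lets a generally healthy child stop a vitamin or mineral taken for a diagnosed deficiency, with no exception or exclusion to prevent it

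*Combined protocol and SAP*

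**What the plan says.** All inclusion criteria in section 5.1 are mandatory. Criterion 3 requires a parent who is "Willing to refrain from giving their child any vitamins, minerals, or herbal supplements of any kind for the duration of the study". The study lasts six months (section 1.1). Criterion 5 sets the health requirement: "Generally healthy do not have any uncontrolled chronic disease".

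The exclusions in section 5.2 that come closest to this point are:

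- Exclusion 1: "Any child with a history of endocrine disorder, heart disease, lung disease, kidney disease, digestive disease or skeletal dysplasia".
- Exclusion 2: "Any pre-existing chronic conditions that would prevent participants from adhering to the protocol, including oncological and psychiatric disorders".
- Exclusion 10: "Unwilling to follow the study protocol".
- Exclusion 12, the only one based on medication, which concerns ADD and ADHD drugs.

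Section 2.2 opens its risk assessment with "There are no predicted risks associated with this product". It then deals with allergy and with interactions, advising that "all medications should be separated by a minimum of 4 hours from taking the test product". It does not mention stopping existing supplements. Section 2.1 states that "In the USA, many people are at risk of vitamin, mineral, and/or other micronutrient deficiencies" and adds that supplements can help to meet some requirements.

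Section 6.2 lists the placebo ingredients, none of which is a vitamin or mineral nutrient. Sections 1.1 and 5.4 put 30 of the 60 children on placebo.

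**The concern.** Barring other supplements is a reasonable restriction when the test product is itself a blend of protein, vitamins and minerals. The difficulty is that the bar is total. For a child already taking iron or vitamin D on a clinician's advice, complying with criterion 3 means stopping treatment, and half of the children then receive a placebo that replaces nothing.

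This is a matter of patient safety. The participants are minors, the interruption can last up to six months, and the risk assessment in section 2.2 covers the product only, so the plan does not weigh this risk. The plan's own rationale treats micronutrient deficiency as common enough to motivate the trial. That statement is about the general population, however, and gives no rate for diagnosed and treated deficiency in children of this age. No effect on the validity of the between-arm comparison is claimed.

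**Working it through.** The plan gives no figure to reproduce on this point. The check is a reading of each rule that might protect the child in question, followed by a short calculation of exposure.

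**Step 1: does any rule stop this child from entering?** Take a generally healthy child with a mild or controlled deficiency, treated with a vitamin or mineral, whose parent agrees to stop.

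| Rule | Effect on this child |
|---|---|
| Inclusion 3 (5.1) | Met, because the parent is willing. It keeps out unwilling parents only. |
| Inclusion 5 (5.1) | Met. It bars uncontrolled chronic disease; a deficiency held in check by a supplement is controlled. |
| Exclusion 1 (5.2) | Not triggered by a simple deficiency. It would catch some deficiencies secondary to digestive, kidney or endocrine disease. |
| Exclusion 2 (5.2) | Not clearly triggered. It applies to conditions that prevent adherence, and once the parent agrees to stop, adherence is possible. |
| Exclusion 10 (5.2) | Not triggered. The family is willing. |
| Exclusion 12 (5.2) | Not relevant (ADD and ADHD drugs). |
| Four-hour spacing of medications (2.2) | Unclear. The plan does not say whether a prescribed vitamin or mineral is a permitted medication or is barred by criterion 3. |

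The child is therefore eligible as written.

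**Step 2: do later safeguards make up for it?** Section 6.4 allows withdrawal at any time, and lets the investigator withdraw a participant when continuing is not in that participant's best interest. Section 1.3 schedules adverse event review. All of these act after enrolment, once the supplement may already have been stopped. A laboratory abnormality is among the reasons for withdrawal in section 6.4, but the schedule in section 1.3 contains no laboratory test and section 6.5 marks in-person diagnostic testing as not applicable. No planned test would show a worsening deficiency.

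**Step 3: how large is the exposure?** Inputs: 60 children, 30 of them on placebo (sections 1.1 and 5.4), allocated equally (section 6.3). Let k be the number of such children enrolled. The documents do not give k, so the values below are assumed.

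- Expected number on placebo = k × 30/60 = k/2.
- P(at least one on placebo) = 1 − C(30,k)/C(60,k).

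| k (assumed) | Expected on placebo | P(at least one on placebo) |
|---|---|---|
| 0 | 0 | 0 |
| 1 | 0.5 | 1 − 30/60 = 0.500 |
| 2 | 1.0 | 1 − 435/1770 = 0.754 |
| 3 | 1.5 | 1 − 4060/34220 = 0.881 |

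Children on the active product would receive vitamins and minerals, at doses the documents do not state. They are not counted.

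**The case against.** The strongest reply is that the case needs a chain of events for which the documents give no frequency: a diagnosed deficiency under treatment, a child who still passes as generally healthy, a parent willing to stop clinician-directed treatment for six months, and allocation to placebo. Criterion 3 asks about willingness and orders no one to stop, so it mainly screens out families who need to continue. An investigator could stretch exclusion 2 to cover a child who must stay on a supplement, since its examples are not exhaustive. A prescribed vitamin could be treated as a medication and continued under the spacing advice in section 2.2. The withdrawal rules limit how long any interruption lasts. The screening questionnaire and consent form cannot be seen, and section 8.2 commits the consent process to explaining the study's potential risks.

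Much of this stands. The number affected is unknown and may be zero, six months is the worst case, and the probabilities above only restate equal allocation for an assumed k. It cannot be said that parents are not told, or that the question is not asked at screening.

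It does not close the gap. The protective readings of exclusion 2 and section 2.2 are possible but not stated, and the unqualified scope of criterion 3 points the other way. Willingness protects a child only when the parent recognises the problem and refuses. Withdrawal acts after the event. At best the plan is ambiguous about whether a minor's treatment may continue, and an eligibility rule should settle that.

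**Conclusion.** The concern holds. As written, a generally healthy child taking a vitamin or mineral for a diagnosed deficiency can enter the trial if the parent agrees to stop it, and then has a 1 in 2 chance of six months on a placebo without vitamin or mineral nutrients. No criterion clearly prevents this, and section 2.2 does not name it as a risk.

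The size cannot be established from the documents. For one to three such children (assumed), the chance of at least one on placebo runs from 50% to 88%; with none enrolled it is zero. These are probabilities of exposure and say nothing about harm. The gap in the text is clear and its frequency is unknown, so confidence is medium. The change should be made because the participants are minors and the remedy costs very little. The exclusion line carries the point; the sentence in section 2.2 is supporting documentation.

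**What to change.** Add to section 5.2 an exclusion for any child currently taking a vitamin or mineral that a clinician has prescribed or advised to treat a diagnosed deficiency or to prevent its recurrence. Confirm this at screening with one question, if it is not already asked. Children who take routine vitamins without a diagnosed deficiency remain eligible under criterion 3, so the restriction on other supplements is kept. Add one sentence to section 2.2 naming interruption of supplements as a risk.

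The cost is one exclusion line, one sentence and possibly one screening question. A few children may not be enrolled. No arm, endpoint or analysis changes.
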